14.2 Clinical Laboratory Variables

Clinical laboratory tests are performed at Screening, Baseline, Weeks 4 and 12/ET visits.

- Chemistry serum tests include the following
 - Sodium (Na), potassium (K), chloride (Cl), phosphorus (P), calcium (Ca), carbon dioxide (CO₂), blood urea nitrogen (BUN), creatinine (CR), uric acid

- Alanine aminotransferase (ALT/SGPT), aspartate aminotransferase (AST/SGOT), gamma-glutamyl transpeptidase (GGT), alkaline phosphatase (ALP), total bilirubin (TBIL), lactate dehydrogenase (LDH)
- HbA1c, glucose
- Albumin (ALB), total protein
- Prolactin
- Creatine kinase (CK)/creatine phosphokinase (CPK)
- Lipid panel
 - Total cholesterol, HDL-cholesterol, triglycerides, LDL-cholesterol, cholesterol/HDL ratio, Non-HDL cholesterol
- Serum pregnancy test for women of childbearing potential
- Vitamin B12 assay (completed only at Screening)
- Hematology tests include the following:
 - Complete blood count (CBC) including:
 - White blood cell (WBC) count
 - Complete differential (relative and absolute)
 - Hematocrit (Hct), hemoglobin, red blood cells (RBC), platelets
 - Reticulocytes
- Urinalysis tests include the following:
 - Blood, RBCs, WBCs, protein, glucose, ketones, specific gravity, pH
 - Urine pregnancy test for women of childbearing potential.

All laboratory test results are from a central laboratory and will be listed. The listings will include date and study day of collection. All units will be displayed in Système International [SI] units. Out of range values will be flagged in the data listings (e.g., 'L' or 'H').

Clinical laboratory values for hematology, chemistry and urinalysis will be summarized by treatment group using descriptive statistics at Baseline, Week 4, and Week 12 visits. The change from Baseline values will also be summarized by treatment group at the Week 4 and Week 12 visits. The overall minimum and maximum post-Baseline observed and change from Baseline values will also be summarized. For hemoglobin, hematocrit and uric acid, the above summaries will be presented for each gender as well as for both genders combined. For urinalysis with categorical results, the number and percentage of subjects will be tabulated by category at Baseline, Week 4, and Week 12 visits. For the categorical urinalysis by-visit

summary, the denominator is the total number of subjects with non-missing values for the given parameter, visit and treatment group.

The laboratory values will also be summarized in shift tables by treatment group, to determine the number and percentage of subjects with values classified as below (low), within (normal) and above (high) normal ranges at Week 4 and Week 12 visits relative to the same classification at the Baseline visit. The shifts from Baseline to overall post-Baseline minimum and overall post-Baseline maximum will also be presented. For the by-visit shift summary, the denominator is the number of subjects with non-missing values at Baseline and the given visit for the given parameter and treatment group. For the summaries of shift to the overall post-Baseline minimum or maximum, the denominator is the number of subjects with non-missing Baseline and at least 1 post-Baseline value for the given parameter and treatment group. For hemoglobin, hematocrit and uric acid, the shift summaries will be presented for each gender as well as for both genders combined.

Number and percentage of subjects with potentially clinically important (PCI) laboratory values at Week 4, Week 12 visits and overall post-Baseline will be summarized by treatment group and by Baseline status (all and within normal range) for selected parameters. PCI criteria are listed in [Table 5](#) and [Table 6](#). For the overall post-Baseline summaries, all post-Baseline values will be considered, including unscheduled and out of window values. Subjects with multiple PCI values for a given parameter will be counted only once for that parameter. For the by-visit summary, the numerator for the percentage is the number of subjects with a post-Baseline PCI laboratory value for the given parameter, visit and treatment group, and the denominator is the number of subjects with non-missing values for the given parameter, visit and treatment group. For the overall post-Baseline summary, the numerator for the percentage is the number of subjects with at least 1 post-Baseline PCI laboratory value for the given parameter and treatment group and the denominator is the number of subjects with at least 1 post-Baseline laboratory value for the given parameter and treatment group. For hemoglobin, hematocrit and uric acid, the count and percentage of subjects with PCI values will be presented for each gender as well as for both genders combined. Subjects with any PCI values will be presented in an additional listing.

Table 5 Criteria for Potentially Clinically Important Laboratory Values – Hematology and Chemistry

Analyte	Conventional Unit	Low PCI Criteria	High PCI Criteria	SI Unit	Low PCI Criteria	High PCI Criteria
Hematology (whole blood)						
Hemoglobin (male)	g/dL	<11	>18	g/L	<110	>180
Hemoglobin (female)	g/dL	<10	>17	g/L	<100	>170
Hematocrit (male)	%	<30	>55	L/L	<0.3	>0.55
Hematocrit (female)	%	<30	>50	L/L	<0.3	>0.5
Leukocyte (White Blood Cell Count)	$\times 10^3/\mu\text{L}$	≤ 2.8	≥ 15	$\times 10^9/\text{L}$	≤ 2.8	≥ 15
Neutrophils	$\times 10^3/\mu\text{L}$	≤ 1.5	No upper limit	$\times 10^9/\text{L}$	≤ 1.5	No upper limit
Platelet Count	$\times 10^3/\mu\text{L}$	≤ 75	≥ 700	$10^9/\text{L}$	≤ 75	≥ 700
Chemistry (serum or plasma)						
ALT (SGPT)	U/L	No lower limit	$\geq 3 \times \text{ULN}$	U/L	No lower limit	$\geq 3 \times \text{ULN}$
AST (SGOT)	U/L	No lower limit	$\geq 3 \times \text{ULN}$	U/L	No lower limit	$\geq 3 \times \text{ULN}$
Total Bilirubin	mg/dL	No lower limit	$\geq 1.5 \text{ ULN}$	umol/L	No lower limit	$\geq 1.5 \text{ ULN}$
BUN	mg/dL	No lower limit	≥ 30.0	mmol/L	No lower limit	≥ 10.71
Creatine Kinase (CK)	U/L	No lower limit	$\geq 3 \text{ ULN}$	U/L	No lower limit	$\geq 3 \text{ ULN}$
Sodium	mEq/L	≤ 125	≥ 155	mmol/L	≤ 125	≥ 155
Potassium	mEq/L	≤ 3.0	≥ 5.5	mmol/L	≤ 3.0	≥ 5.5
Calcium, total	mg/dL	<8.0	>11.0	mmol/L	<2.0	>2.75
Lactate Dehydrogenase (LDH)	U/L	No lower limit	$\geq 3 \times \text{ULN}$	U/L	No lower limit	$\geq 3 \times \text{ULN}$
Alkaline Phosphatase	U/L	No lower limit	$\geq 3 \times \text{ULN}$	U/L	No lower limit	$\geq 3 \times \text{ULN}$
Uric acid (male)	mg/dL	No lower limit	≥ 10.5	umol/L	No lower limit	≥ 624.75
Uric acid (female)	mg/dL	No lower limit	≥ 8.5	umol/L	No lower limit	≥ 505.75
Albumin	g/dL	≤ 2.6	≥ 6.0	g/L	≤ 26	≥ 60
Total Protein	g/dL	≤ 5.0	≥ 10.0	g/L	≤ 50	≥ 100
Chloride	mEq/L	≤ 85	≥ 120	mmol/L	≤ 85	≥ 120
Glucose (random)	mg/dL	≤ 45.1	≥ 200.0	mmol/L	≤ 2.48	≥ 11
Serum Creatinine	mg/dL	Not Applicable	$>1.5 \text{ ULN}$	umol/L	Not Applicable	$>1.5 \text{ ULN}$
Triglycerides	mg/dL	Not Applicable	>300	mmol/L	Not Applicable	>3.39
Gamma-Glutamyl Transferase (GGT)	U/L	Not Applicable	$\geq 3 \text{ ULN}$	U/L	Not Applicable	$\geq 3 \text{ ULN}$

Table 6 Criteria for Potentially Clinically Important Laboratory Values – Urinalysis

Urinalysis (qualitative dipstick)	Low PCI Criteria	High PCI Criteria
Blood (Occult Blood)	Not Applicable	≥ 2
Protein	Not Applicable	≥ 2
Glucose	Not Applicable	≥ 2

The pregnancy results (positive or negative) for female subjects will be presented in a listing.

14.3 Vital Signs

Vital signs are assessed at Screening, Baseline, Weeks 2, 4, 8 and 12/ET visits.

Vital signs including weight, height (only at Screening), and the derived BMI will be summarized by treatment group using descriptive statistics at Baseline and all post-Baseline visits. The change from Baseline values will also be summarized by treatment group at the post-Baseline visits.

Vital sign values will be considered PCI if they meet both the observed value criteria and the change from Baseline criteria listed in [Table 7](#). The number and percentage of subjects with post-Baseline values that are PCI will be summarized by treatment group at each post-Baseline visit and for overall post-Baseline. For the overall post-Baseline summaries, all post-Baseline values will be considered, including unscheduled and out of window values. Subjects with multiple PCI values for a given parameter will be counted only once for that parameter. For the by-visit summary, the numerator for the percentage is the number of subjects with a post-Baseline PCI vital sign for the given parameter, visit and treatment group and the denominator is the number of subjects with non-missing values for the given parameter, visit and treatment group. For the overall post-Baseline summary, the numerator for the percentage is the number of subjects with at least 1 post-Baseline PCI vital sign for a given parameter and treatment group and the denominator is the number of subjects at least 1 post-Baseline vital sign for the given parameter and treatment group. Subjects with any PCI values will be presented in an additional listing.

Table 7 Criteria for Potentially Clinically Important Vital Signs

Vital Sign Parameter	Unit	Criteria ^a		
		Observed Value	And/Or	Change Relative to Baseline
Systolic blood pressure	mmHg	≥180	And	Increase of ≥20
		≤90	And	Decrease of ≥20
Diastolic blood pressure	mmHg	≥105	And	Increase of ≥15
		≤50	And	Decrease of ≥15
Pulse	bpm	≥120	And	Increase of ≥15
		≤50	And	Decrease of ≥15
Weight	kg	Not Applicable		Increase of ≥7%
				Decrease of ≥7%

^a A post-Baseline value is considered as a PCI value if it meets both criteria for observed value and change from Baseline.

14.4 Electrocardiogram (ECG)

Electrocardiogram is performed at Screening, Baseline, Weeks 4 and 12/ET visits. All tracings will be evaluated by a central reading laboratory. ECG data summaries will be performed using the centrally evaluated data.

Observed values of ECG variables (heart rate, PR interval, RR interval, QRS interval, QT interval, and QTc intervals) and the changes from Baseline at each assessment timepoint will be summarized by treatment group at Baseline, Week 4, and Week 12 visits.

QTc intervals include QTcB (Bazett's formula) and QTcF (Fridericia's formula). QTcF will also be categorized into the following categories (msec) and the number and percentage of subjects in each category will be summarized by treatment group at each visit and overall post-Baseline maximum:

- Observed: ≤450, 451 to 480, 481 to 500, and >500
- Change from Baseline: ≤10, 11 to 30, 31 to 60, and >60

Electrocardiogram variable values will be considered PCI if they meet or exceed the upper limit values listed in Table 8. The number and percentage of subjects with post-Baseline PCI values will be summarized by treatment group at each post-Baseline visit and for overall post-Baseline. For the overall post-Baseline summaries, all post-Baseline values will be considered, including unscheduled and out of window values. Subjects with multiple PCI values for a given parameter will be counted only once for that parameter. For the by-visit summary, the numerator for the percentage is the number of subjects with a post-Baseline PCI ECG for the given parameter, visit and treatment group and the denominator is the number of subjects with non-missing values for the given parameter, visit and treatment

group. For the overall post-Baseline summary, the numerator for the percentage is the number of subjects with at least 1 post-Baseline PCI ECG for the given parameter and treatment group and the denominator is the number of subjects with at least 1 post-Baseline ECG value for the given parameter and treatment group. A listing of all subjects with any PCI values will be provided.

Table 8 Criteria for Potentially Clinically Important ECG Values

ECG Parameter	Unit	High PCI Criteria
QRS Interval	msec	≥120
PR Interval	msec	≥220
QTcB or QTcF	msec	>500
QTcB or QTcF: change from Baseline	>60 msec	

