(including postural), headache, and somnolence (drowsiness). Common GI disturbances included dyspepsia, nausea, constipation, and vomiting; severe nausea and vomiting were dose limiting in a few cases. Reported psychiatric conditions included such events as agitation, insomnia, and confusional state. In controlled studies of pimavanserin in subjects with PDP, the most frequent TEAEs experienced by subjects in the pimavanserin 34 mg group compared with the placebo group were urinary tract infection (UTI) (7.4% pimavanserin 34 mg vs. 6.9% placebo), nausea (6.9% pimavanserin 34 mg vs. 4.3% placebo), peripheral edema (6.9% pimavanserin 34 mg, 2.2% placebo), fall (6.4% pimavanserin 34 mg vs. 9.1% placebo), and confusional state (5.9% pimavanserin 34 mg vs. 2.6% placebo). In the long-term open-label studies in subjects with PDP, the most frequent adverse events (AEs) include fall (29.3%), UTI (18.5%), hallucination (14.5%), decreased weight (12.4%), and confusional state (11.0%). It is difficult to interpret these incidence rates in the absence of a concurrent control group, but the overall incidence appears within what would be expected in subjects with the underlying neurodegenerative disease, psychosis, and advanced age.

Clinical and non-clinical safety pharmacology studies of pimavanserin suggest a potential risk for QT prolongation. The magnitude of effect in humans has been assessed in a thorough QT study with doses of pimavanserin ranging from 17 to 68 mg and in the Phase 3 PDP program with a clinical dose of 34 mg. An average prolongation of approximately 5-8 milliseconds (ms) was observed. No clinically significant patterns have been observed in serious adverse events (SAEs) and there has been no evidence of pimavanserin-related laboratory abnormalities. As of 30 October 2015, 67 subjects have died during study participation with the majority of deaths considered not related or unlikely related to study drug. Five of these deaths occurred in 6-week double-blind studies (1 subject received placebo, 1 subject received 10 mg pimavanserin, and 3 subjects received 34 mg pimavanserin), and 62 deaths occurred in the multi-year, long-term open-label extension studies where the majority of subjects have been treated with pimavanserin for greater than 2 years.

Additional information is provided in the Investigator's Brochure.

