### **9.8.4 Electrocardiogram**

ECG parameters at baseline and at Weeks 4 and 12 will be summarized by treatment group. Change from baseline values will also be summarized. Categorical analyses will be conducted on the incidence of subjects with prolonged QTc intervals and changes in QTc intervals in accordance with ICH guidelines and based on the FDA E14 Guidance Document.

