5 DATA HANDLING CONVENTIONS

All data collected in the study will be listed.

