5.1 General Data Reporting Conventions

For continuous variables, the following summary statistics will be provided: number of subjects, mean, standard error of the mean (SE), standard deviation (SD), minimum, maximum and median. Unless specified otherwise, means, medians, and confidence intervals (CIs) will be presented to one more decimal place than the raw data, and the standard deviations and standard errors will be presented to 2 more decimal places than the raw data. Unless specified otherwise, all confidence intervals will be 2-sided 95% confidence intervals.

For categorical variables, summaries will include the number and percentage of subjects in each category, using the number of subjects with non-missing values as the denominator for the percentages (unless otherwise specified). Categories with zero counts will not have zero percentages displayed. Percentages will be presented with 1 decimal place.

When converting number of days to months, it will be calculated by dividing the number of days by 365.25 and then multiplying by 12. When converting number of days to years, the number of days will be divided by 365.25.

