5.3 Analysis Visit Windows

Baseline will be defined as the last non-missing result, including results from repeated and unscheduled measurements, before dosing.

Efficacy, safety, and PK assessments will be summarized by analysis visit as presented in Table 4 below.

Table 4 Analysis Visit Windows

Analysis Visit Name	Target Study Day ¹	Study Day Interval
Baseline	1	≤ 1
Week 2	15	2 to 21
Week 4	29	22 to 42
Week 8	57	43 to 70
Week 12	85	71 to 99
Follow-up	115	≥ 100

¹ study day = assessment date - first dose date + 1 if the assessment date \geq first dose date, otherwise study day = assessment date - first dose date. Study day 1 is the day of first administration of study drug (pimavanserin or placebo).

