14 SAFETY ANALYSES

The safety summaries will be presented based on the Safety Analysis Set using actual treatment. Safety variables include adverse events (AEs), clinical laboratory variables, vital signs, physical examinations, electrocardiogram (ECG) and Global Clinician Assessment of Suicidality (GCAS) variables. Safety variables will be summarized by treatment group using descriptive statistics.

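### SAP 14.4 reports QTcF by arm only: it plans no dose-minus-placebo difference with an interval and no contrast adjusted for pre-treatment QTcF, so precision available from collected ECGs goes unused

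*SAP*

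**What the plan says.** SAP 14 sets the general rule for safety: "Safety variables will be summarized by treatment group using descriptive statistics". Within it, SAP 14.4 covers the QTc intervals in three ways.

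- **Continuous summaries.** Observed values "and the changes from Baseline at each assessment timepoint will be summarized by treatment group at Baseline, Week 4, and Week 12 visits". SAP 5.1 defines a continuous summary as "number of subjects, mean, standard error of the mean (SE), standard deviation (SD), minimum, maximum and median".
- **QTcF categories.** Counts of observed value and of change, where "subjects in each category will be summarized by treatment group at each visit and overall post-Baseline maximum".
- **Potentially clinically important values.** Counts by arm of QTcF above 500 ms or increased by more than 60 ms, with a listing of the subjects concerned.

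Protocol 9.8.4 matches: "ECG parameters at baseline and at Weeks 4 and 12 will be summarized by treatment group". SAP 19 records no change from the protocol. SAP 5 adds "All data collected in the study will be listed".

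On pre-treatment data, SAP 5.3 states: "Baseline will be defined as the last non-missing result, including results from repeated and unscheduled measurements, before dosing". ECGs are taken in triplicate at Screening and singly at Day 1, Week 4 and Week 12 (Protocol 6.2.5; SAP Table 1, footnote f). SAP 5.3.2 averages a triplicate into one assessment.

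On the size of the risk, Protocol 1.2 reports from a thorough QT study and the Phase 3 Parkinson's disease psychosis program: "An average prolongation of approximately 5-8 milliseconds (ms) was observed".

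**The concern.** The stated purpose is to evaluate safety as well as efficacy against placebo. For a drug with an expected mean QT shift of 5-8 ms, the informative quantity is the placebo-corrected mean change and its uncertainty. Counts above 500 ms or of changes above 60 ms respond weakly to a shift of that size. The plan leaves the reader to form the contrast from separate arm tables.

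The no-testing rule does not explain the omission. Under that rule the SAP gives LS mean differences with 95% CIs for the modelled efficacy scores (SAP 12, 13.1), responder differences with CIs (13.4), and odds ratios versus placebo with 95% CIs for SAEs and death (14.1). An estimate with an interval and no p-value is already how this SAP reports.

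What is at stake is precision. Randomization stopped at 111, so no more can come from sample size. Each completer has four ECG sessions, but a change table uses only two at a time: Baseline and one later visit.

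**Working it through.** The plan states no QTcF precision figure, so there is none to reproduce.

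**Inputs from the documents.** 111 randomized 1:1:1, so 111/3 = 37 per arm. Screening is a mean of three tracings; Day 1, Week 4 and Week 12 are single tracings. QTcF above 460 ms is excluded when QRS is below 120 ms (Protocol 4.1.2).

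**Assumed inputs.** The documents give no variances. The middle setting is between-subject SD 17 ms, day-to-day SD 9 ms and within-session SD 8 ms.

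**Variance components.** Between-subject B = 17² = 289. Noise of a single tracing V = 81 + 64 = 145. Noise of the Screening mean S = 81 + 64/3 = 102.3.

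**Residual variances with no drift, dropout or washout.**

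- Raw Week 12 change: 2V = 290.
- A subject's true level given Baseline: 289 − 289²/434 = 96.6, where 434 = B + V.
- The true level given Baseline and Screening: 1/(1/289 + 1/145 + 1/102.3) = 49.7.
- An adjusted single visit adds V = 145. An adjusted two-visit average adds V/2 = 72.5.
- Raw two-visit average change: V + V/2 = 217.5.

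**95% half-width of dose minus placebo** = 1.98 × √(2 × variance/37).

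| Contrast | Variance | Half-width (ms) |
|---|---|---|
| Week 12, raw change | 290 | 7.8 |
| Week 12, Baseline covariate | 241.6 | 7.2 |
| Week 12, Baseline and Screening | 194.7 | 6.4 |
| Two-visit average, raw change | 217.5 | 6.8 |
| Two-visit average, Baseline covariate | 169.1 | 6.0 |
| Two-visit average, Baseline and Screening | 122.2 | 5.1 |

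The closed form ignores the 460 ms limit and the small cost of estimating slopes. Simulation with the limit imposed and a mean of 425 ms (3,000 replicates per setting) gives 7.8, 6.5 and 5.2 ms for the first, third and last rows.

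**Sensitivity.** Simulated half-widths (ms) over between-subject SD 15-20, day-to-day SD 6-12 and within-session SD 6-10 ms, adjusting for both covariates:

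| Scenario | Raw Week 12 | Adjusted Week 12 | Adjusted average | Per-visit variance cut |
|---|---|---|---|---|
| No drift, dropout or washout | 5.4-10.0 | 4.6-8.4 | 3.6-6.6 | 28-31% |
| 30% lose a 15 ms drug effect between Screening and Baseline | 5.4-10.1 | 4.8-8.5 | 3.9-6.7 | 22-30% |
| That washout, 15% loss per arm, subject drift SD 8-12 ms | 7.1-12.5 | 6.5-11.3 | 5.6-9.5 | 8-28% |

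At the middle setting with drift SD 10 ms, the last scenario gives 10.0, 9.0 and 7.4 ms. The 480 ms limit for QRS of 120 ms or more was not modelled.

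**Like for like.** The average and the Week 12 change are different estimands, so the fair comparator for the adjusted average is the raw average. That variance cut is 39.5-41.0% by simulation in the first scenario (1 − 122.2/217.5 = 44% in the closed form) and falls to 8.9% with dropout, washout and drift SD 12 ms.

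**What the planned tables already allow.** At one visit, n, mean and SD give the unadjusted difference and its interval. For the two-visit average, the SE cannot exceed the mean of the two visit SEs. A reader can therefore form a conservative interval: 7.8 ms at the middle setting, against 6.8 ms exact. The exact interval needs the covariance between the visits, which is not tabulated. The adjusted contrast cannot be recovered from the tables at all.

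**The case against.** The strongest reply is that this asks for an extra table and repairs no defect. Safety is an exploratory, descriptive objective, and SAP 14.4 follows Protocol 9.8.4. Laboratory values and vital signs are also reported by arm. The SAE and death contrasts have their own anchor, because Protocol 7.11 has the safety committee compare those rates formally. The mean QT effect was already measured at 17-68 mg, a range that contains both doses here. This trial takes single tracings with no required timing relative to dose. Individual risk is covered by the categories, threshold counts, listings, exclusions and co-medication limits. The documents name no decision that a narrower interval would change.

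Most of that stands, and it fixes the weight of the point as an optional improvement. It does not remove the point: the data are already collected and the SAP's own style accommodates the estimate.

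A reader might infer more than the documents support:

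- **That no pre-treatment adjustment is made.** Change from Baseline subtracts the pre-treatment value. Only adjustment as a covariate is absent.
- **That the planned summaries are biased or give no interval.** Randomization makes the raw contrast unbiased, its per-visit interval follows from the tables, and anyone holding the listings could fit the model.
- **That variance falls by more than half.** Such a figure (54-58% in the most favourable scenario) sets an adjusted average against a raw single-visit change.
- **That a drug stopped after Screening biases the adjusted contrast.** Antipsychotic washout (Protocol 3.1) and citalopram or escitalopram reduction (Appendix C) happen before randomization. They weaken the Screening covariate but do not bias the comparison.

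**Conclusion.** The point holds as a gain in precision for a descriptive safety summary. The omission is clear in both documents. It corrects no error and would not be expected to separate the two doses.

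The size rests wholly on assumed variances. At the middle setting without drift, dropout or washout, the Week 12 half-width falls from about 7.8 to 6.4 ms. Reporting the two-visit average as well brings it to about 5.1 ms, set against an expected effect of 5-8 ms. Part of the gain comes from the Screening covariate: with Baseline alone the figures are 7.2 and 6.0 ms. With drift, dropout and washout, the adjusted Week 12 half-width is about 9.0 ms, still wider than the expected effect, and the per-visit variance cut can be as small as 8%.

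**What to change.** Keep every table in SAP 14.4 and add one paragraph to this effect:

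- **Model.** MMRM of QTcF change from Baseline at Weeks 4 and 12 in the Safety Analysis Set by actual treatment, with treatment, visit, treatment-by-visit, Baseline QTcF, Screening triplicate-mean QTcF and geographic region.
- **Estimation.** Unstructured covariance, Kenward-Roger degrees of freedom, observed margins and the convergence fallback of SAP 13.1.
- **Output.** Each dose's LS mean difference from placebo with a 95% CI at Week 4, at Week 12 and averaged over the two, with no p-values. The per-visit rows show whether the effect differs between visits.
- **Missing pre-treatment values.** If Screening QTcF is missing, or the Day 1 ECG is missing so that Baseline is the Screening value, keep the subject and use the available value for both covariates.

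A simulation of this mean model with common covariate slopes (1,500 replicates, three variance settings by three scenarios) gave an averaged contrast of 6.42-6.60 ms for a true 6.5 ms, and 94.2-95.9% coverage.

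The cost is one more model and one more table, for a modest and assumption-dependent gain. No new data, visits or subjects are needed. The Baseline used in the category and threshold tables is unchanged, and the addition is consistent with the plan's rule against hypothesis testing.

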#### **4.1.2 Exclusion Criteria**

1. The agitation/aggression is attributable to concomitant medications, environmental conditions, substance abuse, or active medical or psychiatric condition
2. Has a current major depressive disorder episode (within 3 months) according to the Diagnostic and Statistical Manual of Mental Disorders - Fifth Edition (DSM-5) criteria

3. Treatment with an antipsychotic medication within 2 weeks of Baseline visit or 5 half-lives, whichever is longer  
Investigators should not withdraw a subject's prohibited medication for the purpose of enrolling them into the study unless discontinuation of the medication is deemed to be clinically appropriate (e.g., symptoms are not well-controlled or the subject cannot tolerate the current medication).
4. Has brain abnormalities seen on an MRI or CT scan (brain imaging) taken during or subsequent to diagnosis of probable AD, that can be attributed to diseases or processes other than AD, including but not limited to:
  - multiple lacunar infarcts or evidence of a single prior infarct  $>1 \text{ cm}^3$ ;
  - intracranial mass lesion (including but not limited to meningioma [ $>1 \text{ cm}^3$  with evidence of peritumoral edema]); or
  - glioma, vascular malformation, or macrohemorrhage.
5. Subject or study partner/caregiver has a medical condition (e.g., hearing, vision impairments) that would impair the ability to perform the study assessments.
6. Subject requires treatment with a medication prohibited by the protocol (see [Section 5.7](#), [Appendix C](#), and [Appendix D](#))
7. Subject has had a myocardial infarction within the last 6 months prior to Screening
8. Subject has a known history or symptoms of long QT syndrome
9. Subject has a QRS interval  $<120 \text{ ms}$  and whose Fridericia's corrected QT interval (QTcF) is  $>460 \text{ ms}$  at Screening or at Baseline **OR** subject has a QRS interval  $\geq 120 \text{ ms}$  and QTcF is  $>480 \text{ ms}$  at Screening or at Baseline
10. Has clinically significant laboratory abnormalities that in the judgment of the Investigator or Medical Monitor would jeopardize the safe participation of the subject in the study
11. Has a history of a significant psychotic disorder prior to or concomitant with the diagnosis of probable AD including, but not limited to, schizophrenia or bipolar disorder
12. Subject is bedridden or has any significant medical condition that is unstable and that would either:

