### *Restricted under certain conditions:*

- Citalopram and escitalopram are restricted to a maximum dose of 20 mg a day. If it is clinically appropriate, subjects on a higher dose of citalopram or escitalopram should be titrated down to 20 mg a day prior to Baseline.
- The medications listed are **ONLY** allowed if:
  - the subject has a baseline ECG with a QTcF <425 ms **OR**
  - the subject has a QTcF <450 ms at Baseline **AND** QRS duration  $\geq$ 120 ms (e.g., subjects with right bundle branch block [RBBB] or left bundle branch

block [LBBB], an intraventricular conduction disturbance [IVCD], or ventricular pacing)

Antimicrobials, antifungals, and antimalarials	Antidepressants	Others

• artenimol/piperaquine

• bedaquiline

• gemifloxacin

• norfloxacin

• ofloxacin

• quinine

• roxithromycin

	

• clomipramine

• desipramine

• imipramine

• mirtazapine

• nortriptyline

	

• felbamate

- The medications listed above are **not allowed** if a subject has a QTcF  $\geq 425$  ms and a QRS duration  $< 120$  ms at baseline.

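### The ECG counts of potentially clinically important QRS and PR values ignore Baseline, so stable conduction abnormalities that the entry criteria allow are mixed with new ones

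*SAP*

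**What the plan says.** SAP 14.4 sets the rule: "Electrocardiogram variable values will be considered PCI if they meet or exceed the upper limit values listed in Table 8". Table 8 lists QRS ≥120 msec, PR ≥220 msec, QTcB or QTcF >500 msec, and a QTcB or QTcF change from Baseline >60 msec. Only the last row refers to Baseline. On reporting, "The number and percentage of subjects with post-Baseline PCI values will be summarized by treatment group at each post-Baseline visit and for overall" post-Baseline, and for the overall summary "the denominator is the number of subjects with at least 1 post-Baseline ECG value for the given parameter and treatment group".

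On entry, the second limb of exclusion 9 (Protocol 4.1.2) removes a subject with QRS ≥120 ms only when QTcF is >480 ms. The first limb, which opens "Subject has a QRS interval" below 120 ms, caps QTcF at 460 ms. Neither the inclusion nor the exclusion criteria give a PR limit. Appendix C, item 6, has a medication rule for subjects whose QRS duration is ≥120 ms, with examples that start "subjects with right bundle branch block [RBBB] or left bundle branch" block and go on to intraventricular conduction disturbance and ventricular pacing.

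The SAP treats its other PCI counts differently. Laboratory PCI values are summarized by treatment group and "by Baseline status (all and within normal range) for selected parameters" (14.2), with shift tables as well. In 14.3, "Vital sign values will be considered PCI if they meet both the observed value criteria and the change from Baseline criteria"; in Table 7 this dual condition applies to blood pressure and pulse.

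**The concern.** The QRS value that Table 8 flags is the same 120 ms value that exclusion 9 allows at entry. A subject who enters with a fixed bundle branch block and stays unchanged will normally be counted as PCI at Week 4, at Week 12 and overall. The same holds for a subject who enters with PR ≥220 ms. The reported percentage then adds two different things together: who entered with a conduction abnormality, and who developed one on study. The first says nothing about the drug, and with about 37 subjects per arm a handful of such subjects can move the percentage visibly.

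There is also a wording conflict in the same section. The sentence defining PCI includes values equal to the limit, while Table 8 uses strict inequalities for both QTc rows.

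**Working it through.** **The rule against the entry criteria**

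| Parameter | Flagged post-Baseline (Table 8) | Allowed at entry | Baseline used in the PCI count? |
|---|---|---|---|
| QRS | ≥120 msec | ≥120 ms, if QTcF ≤480 ms | No |
| PR | ≥220 msec | No limit stated | No |
| QTcF, observed | >500 msec | ≤460 ms (QRS <120) or ≤480 ms (QRS ≥120) | Not needed for eligible subjects |
| QTcF, change | >60 msec | Not applicable | Yes |

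The gap is confined to QRS and PR. An eligible subject cannot enter with QTcF above 500 ms, so a Baseline split of that row would be empty.

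**Illustration of size (QRS)**

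The plan attaches no figure to this rule, so there is nothing to reproduce. Inputs:
- Subjects per arm: 111 randomized 1:1:1 (SAP 3.1 and 3.5), so 111/3 = 37. The real denominator is smaller if some subjects have no post-Baseline ECG.
- p, the share with QRS ≥120 ms at Baseline: not in the documents. Assumed 5% to 20%, all persisting.
- q, the share of the remaining subjects who newly cross the limit: not in the documents. Assumed 0% or 5%.

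Formulas:
- Expected pre-existing cases per arm = 37 × p.
- Proportion reported under the current rule = p + (1 − p) × q.
- Share of the reported count that is pre-existing = p / [p + (1 − p) × q].
- Chance imbalance = P(|X₁ − X₂| ≥ 3), with X₁ and X₂ independent Binomial(37, p). Three subjects are 3/37 = 8.1 percentage points.

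| p | Pre-existing per arm | Reported, q = 0 | Reported, q = 5% | Pre-existing share, q = 5% | P(arms differ by ≥3 on pre-existing cases alone) |
|---|---|---|---|---|---|
| 5% | 1.85 | 5.0% | 9.8% | 51% | 17% |
| 10% | 3.70 | 10.0% | 14.5% | 69% | 33% |
| 15% | 5.55 | 15.0% | 19.2% | 78% | 41% |
| 20% | 7.40 | 20.0% | 24.0% | 83% | 47% |

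Worked row, p = 10% and q = 5%: 0.10 + 0.90 × 0.05 = 0.145, and 0.10/0.145 = 0.69.

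Restricted to subjects below the limit at Baseline, the expected proportion is q itself: 0% or 5%, whatever p is. The denominator falls to 37 × (1 − p), that is from 37 to about 35.2, 33.3, 31.5 or 29.6.

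**The boundary conflict**

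A QTcF of exactly 500 msec is PCI by the sentence, not PCI by Table 8, and falls in the 481 to 500 category of the same section. A change of exactly 60 msec is PCI by the sentence, not by the table, and falls in the 31 to 60 category. Table 8 and the categories agree with each other; the sentence is the odd one out.

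**The case against.** The strongest reply is that nothing here is mislabelled and that the information needed is largely planned already. The counts are called post-Baseline PCI values; the SAP defines treatment emergence only for adverse events (14.1). Section 14.4 summarizes PR and QRS, observed and as change from Baseline, and under 5.1 those summaries include the mean, SD, median, minimum and maximum. A subject with a fixed block and no drug effect contributes a change near zero. Subjects with PCI values are listed, and medical history is tabulated by arm (SAP 9). Even the laboratory model keeps a count in all subjects. Efficacy and safety summaries are descriptive, and no stated decision rule uses these counts.

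Most of this stands, and it sets the weight of the point. What it does not do is supply the missing count. Group means can conceal a few new conduction blocks, and a listing gives cases but no rate or denominator.

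A reader might infer more: that pre-existing disease will be reported as an effect of treatment, or that a drug signal will be systematically hidden or created. The documents do not support that. Randomization balances pre-existing abnormalities in expectation, which leaves dilution and chance imbalance. Nor does the average prolongation of about 5-8 ms in Protocol 1.2 add weight, because it concerns QT; the documents report no PR or QRS effect. QTcF already has a change criterion and categories for observed value and change.

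**Conclusion.** The point holds as a reporting weakness of minor to moderate importance, confined to the QRS and PR rows. It is most direct for QRS, where the entry criterion and the flag use the same value. For PR it rests on the absence of a stated entry limit; general exclusions such as unstable medical conditions may remove some of these subjects. Efficacy summaries are untouched.

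The mixing of old and new abnormalities follows from the text alone. Its size does not. The figures of about 1.9 to 7.4 subjects per arm, and the 17% to 47% chance of a difference of three or more, depend on assumed Baseline prevalences of 5% to 20%, on 37 evaluable subjects per arm, and on every pre-existing case persisting. They were worked for QRS; nothing in the documents allows a separate PR estimate.

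The conflict between the sentence and Table 8 is real but affects only values of exactly 500 msec or changes of exactly 60 msec. It still deserves one unambiguous rule, since listings of potentially clinically important QTcF results also go to the Safety Monitoring Committee (SAP 17).

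**What to change.** Two changes to SAP 14.4:

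1. Present the QRS and PR PCI counts, by visit and overall, in two blocks: all subjects, and subjects below the limit at Baseline, each with its own denominator. This follows the laboratory approach in 14.2. No split is needed for QTcF >500 msec, because entry QTcF is capped.
2. Reword the defining sentence so that a value is PCI when it meets the criteria listed in Table 8, in place of 'meet or exceed'. The operators in the table then govern, and they match the QTcF categories in the same section.

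The cost is SAP wording and one extra row block in one table. No new data are needed, since Baseline ECGs are already scheduled and centrally read. The downside is a slightly smaller denominator in the Baseline-restricted rows.
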